9.6.1 Adverse Events

Adverse events will be coded to System Organ Class and preferred term using the Medical Dictionary for Regulatory Activities (MedDRA) version adopted at the start of the double-blind study in which the subject previously participated (Version 15.0 or later).

Adverse events will be regarded as treatment-emergent (TEAE) if they start on or after the first dose of study drug administration in the open-label study or if they were present prior to the first date of study drug administration and increased in severity or relationship to study drug while on study treatment. Those that resolved prior to the first dose or were ongoing at the same intensity and relationship will be regarded as pre-treatment AEs and not summarized.

Tabular summaries are described below, with the number and percentage of subjects reporting each type of event presented. If a subject reports the same preferred term more than once, it is counted only once within that category. Further, for a given tabulation, the preferred term will only be counted once in its worst severity, greatest relationship to treatment, and worst action taken.

Pre-study AEs, those present at the time of the first dose of study drug administration, will be presented separately.

An overall summary table of TEAEs will be produced showing the number and percent of subjects with the following: TEAE, severe intensity TEAE, TEAE related to study drug, AESIs, serious TEAE, TEAE with outcome of death, and TEAE leading to interruption, dose reduction, or discontinuation from the study. In addition, the summary table will include the number of TEAEs, severe TEAEs, TEAEs related to study drug, and serious TEAEs.

Separate summaries of incidences (number and percentage of subjects) of all individual TEAEs and the subsets of drug-related TEAEs, TEAEs that are severe in intensity, serious TEAEs, and TEAEs leading to change in dose will be provided.

The subset of TEAEs that have an onset more than 7 days after the last dose of study drug will be considered post-treatment. An overall summary table of the number and percent of subjects with post-treatment AEs will be prepared.

All AEs will be presented in a data listing. In addition, listings also will be provided for SAEs, AEs leading to death, AEs leading to discontinuation of study drug, AEs leading to dose reduction and/or interruption, and any other AEs that are of special interest (to be defined prior to database lock).

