## **7. SAFETY ANALYSES**

### **7.1 Adverse Events**

There are two CRFs contributing adverse event data.

- **Prior Study – Adverse Events CRF:** All adverse events as recorded during prior studies 005, 007 and 015 will be automatically uploaded to the Prior Study – Adverse Events CRF and adverse events recorded during the 008 study will be recopied from the 008 records by the site to the Prior Study – Adverse Events CRF. The only field that can be modified by the site is the OLEX end date as applicable. Additionally there is a comment field where text can be entered by site.
- **Adverse Event CRF:** New adverse events or changes to an existing adverse event will be recorded on the Adverse Event CRF.

Adverse events will be coded to SOC and PT using MedDRA (version 16.0). The coding process is described in the Data Management Plan.

AEs are grouped as follows and source(s) of data identified:

1. **Prior AEs:** AEs that were ongoing at the end of the prior study but that resolved before Day 1 of dosing in 020 or that started and resolved during the gap between studies. The source would be both the Prior Study – Adverse Events CRF and the (020) Adverse Event CRF.
2. **Pre-existing AEs:** AEs that were ongoing on Day 1 of dosing in 020 - source is the Prior Study – Adverse Events CRF. The source would be both the Prior Study – Adverse Events CRF and the (020) Adverse Event CRF.

3. Study-emergent AEs: AEs that started on or after Day 1 of dosing in 020, excluding post-treatment AEs (defined in #5 below). The source would be the (020) Adverse Event CRF.
4. All AEs: Whether pre-existing or study-emergent (merge of AEs that were ongoing on Day 1 of dosing) excluding post-treatment AEs. Sources are the Prior Study – Adverse Events CRF and the (020) Adverse Event CRF (note, this is a merge of #2 and 3 above *only*).
5. Post-treatment AEs: The study-emergent AEs (3# above) that have an onset more than 14 days after the last dose of study drug or that worsen in intensity or treatment attribution following discontinuation more than 14 days after the last dose of study drug.

The tabular summaries will be provided for AEs, with the number and percentage of subjects reporting each type of event. If a subject reports the same preferred term more than once, it is counted only once within that category. Further, for a given tabulation, the preferred term will only be counted once at its worst severity and strongest relationship to treatment.

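### The adverse-event categories in SAP 7.1 do not implement the protocol's treatment-emergent definition, and no planned table is defined on that set

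*SAP*

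**What the plan says.** **Protocol 9.6.1.** An AE is treatment-emergent if it starts on or after the first open-label dose, or if it was "present prior to the first date of study drug administration and increased in severity or relationship to study drug while on study treatment". The section then requires a table on that set: "An overall summary table of TEAEs will be produced showing the number and percent of subjects with the following" (a list of AE types follows). Events already present at first dose are kept apart: "Pre-study AEs, those present at the time of the first dose of study drug administration, will be presented separately". Post-treatment AEs are a part of the TEAEs, defined by onset: "The subset of TEAEs that have an onset more than 7 days after the last dose of study drug will be considered post-treatment".

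**SAP 7.1.** AEs are sorted into five numbered groups:

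- Category 2: every AE ongoing on Day 1, worsened or not.
- Category 3: "Study-emergent AEs: AEs that started on or after Day 1 of dosing in 020, excluding post-treatment AEs (defined in #5 below").
- Category 4: categories 2 and 3 merged, again without post-treatment AEs.
- Category 5 (post-treatment): study-emergent AEs with onset more than 14 days after last dose, "or that worsen in intensity or treatment attribution following discontinuation more than 14 days after the last dose of study drug".

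The main summaries are planned for categories 2 to 4. Category 5 gets a system organ class and preferred term (SOC/PT) table only.

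**Data capture, SAP 7.1.** For AEs mapped from the prior study, "The only field that can be modified by the site is the OLEX end date as applicable", apart from a comment field. Otherwise, "New adverse events or changes to an existing adverse event will be recorded on the Adverse Event CRF". A same-event rule counts records with the same preferred term as one event if they overlap, if the earlier one has no end date, or if they lie no more than two days apart.

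**The concern.** Long-term safety and tolerability is the objective that the data can evaluate, and the protocol's main AE summary is a TEAE table. A pre-existing condition that worsens on the drug is one of the signals the protocol's second criterion is meant to catch. Under the SAP such an event sits in category 2 and, mixed with AEs that never changed, in category 4. Neither separates it.

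Category 5 raises a second problem. It is drawn from category 3, while category 3 is defined by excluding category 5, so neither can be derived first. Its worsening criterion could also move an AE that began on treatment into the post-treatment group. The SAP's own footnote to Table 14.3.2.15.1 (Appendix G) defines post-treatment by onset only, so the programmer has two conflicting instructions.

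**Working it through.** **Step 1: place AE courses under both sets of rules.** The inputs are the definitions above. Three assumptions are needed. The circularity is resolved by drawing category 5 from all AEs with onset on or after Day 1. In row C the worsening is not re-entered as a new record. In row E the late worsening can be identified on the same or a joined record.

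| AE course | Protocol TEAE | Protocol post-treatment | Cat. 2 | Cat. 3 | Cat. 4 | Cat. 5 |
|---|---|---|---|---|---|---|
| A. Resolved before Day 1 | no | no | no | no | no | no |
| B. Ongoing on Day 1, unchanged | no | no | yes | no | yes | no |
| C. Ongoing on Day 1, worsens on treatment | yes | no | yes | no | yes | no |
| D. Onset on treatment | yes | no | no | yes | yes | no |
| E. Onset on treatment, worsens 20 days after last dose | yes | no | no | no | no | yes |
| F. Onset 5 days after last dose | yes | no | no | yes | yes | no |
| G. Onset 10 days after last dose | yes | yes | no | yes | yes | no |
| H. Onset 20 days after last dose | yes | yes | no | no | no | yes |
| I. Ongoing on Day 1, worsens only 20 days after last dose | no | no | yes | no | yes | no |

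The protocol TEAE set is {C, D, E, F, G, H}. Against it:

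- Category 3 = {D, F, G}: 3 of the 6.
- Category 4 = {B, C, D, F, G, I}: 4 of the 6, plus 2 non-TEAEs.
- Category 5 = {E, H}; E is not post-treatment under the protocol.
- Categories 3 + 5 = {D, E, F, G, H}: C is missing.
- Categories 4 + 5: all 6, plus the 2 non-TEAEs B and I.

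No category, and neither union, equals the TEAE set. None equals the TEAE set less its post-treatment part, {C, D, E, F}.

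**Step 2: can row C reach category 3 by re-entry?** The mapped record cannot be regraded, so the worsening would need a new record on the 020 AE form starting on or after Day 1. With an unchanged preferred term, the site may close the mapped record within two days of the new start or leave it open. Either way the same-event rule joins the two. The rule governs counting; it does not say which start date, and so which category, the joined event takes.

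**Step 3: count the tables (SAP Appendix F).** Families 14.3.2.1 to 14.3.2.14 each have an all-subjects version and a version for non-users of AChEI/memantine.

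- Category 2: 14 × 2 = 28.
- Category 3: 14 × 2 = 28.
- Category 4: 14 × 2 = 28, plus 6 by prior treatment = 34.
- Category 5: 2.
- Total: 28 + 28 + 34 + 2 = 92. Defined on the protocol TEAE set: 0.

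Under row E's condition the AE would be absent from 28 + 34 = 62 tables and could appear only in the 2 category 5 tables.

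**Step 4: cut-off.** At the target follow-up date (28 days after last dose), 28 − 7 = 21 days count as post-treatment under the protocol and 28 − 14 = 14 under the SAP. Onsets on the 7 days from day 8 to day 14 change group. These are not upper limits, because Protocol 7.1 requires AE follow-up past that visit if needed.

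**The case against.** **Changes do have a route into category 3.** The 020 AE form takes changes to existing AEs, and a worsening entered with a start on or after Day 1 meets category 3 as written. This stands: the fault is a missing start-date and joining rule, not a demonstrated loss of events.

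**Row E is narrow.** The fields listed in Protocol 7.1 include start and stop dates, intensity and relationship, but no date of change. Without one, late worsening on a single record cannot be dated; entered as a separate, unjoined record, it leaves the first record in category 3. This also stands, so the 62-table consequence is conditional.

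**A reader might infer that treatment-emergent events, or withdrawals caused by them, vanish from the report.** The documents do not support that. Categories 4 and 5 together hold every TEAE. An AE withdrawal also appears by reason in the disposition and discontinuation tables (14.1.1.1 and 14.1.2.1). The legend of Listing 16.2.7.3.1 carries a post-treatment flag, although the text of 7.1 names only study-emergent AEs for that listing.

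**A reader might infer from SAP section 1, which limits reporting to study-emergent data, that category 3 alone decides what is reported.** It does not: category 2 and 4 tables are planned as well.

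**The 14-day cut-off may be deliberate.** SAP 7.2 treats laboratory results from 14 days after last dose as post-treatment, and Appendix A uses the same limit for the follow-up window. A longer cut-off keeps more AEs in the on-treatment tables. Protocol section 9 and SAP section 9 allow changes to be documented in the study report. This stands against treating 14 days as an error in itself. It does not settle the circularity, the conflict with the SAP's own footnote, or the category of a joined event, all of which must be decided before programming.

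**The study is single-arm and descriptive.** True, but here the definition of the set determines the result.

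**Conclusion.** SAP 7.1 does not carry out the protocol's TEAE definition. That follows from the wording alone: one criterion is missing from category 3, one is added to category 5, those two categories are defined from each other, and the cut-offs differ. As a result, the overall TEAE table that Protocol 9.6.1 requires cannot be read from any of the 92 planned AE tables.

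The count of 0 in 92 shows scope, not bias: most of the tables repeat a few shells, and one missing criterion is enough to exclude them all. A claim that TEAE incidence will be understated would go too far, since number and direction depend on how sites record worsening. Row C's placement assumes no re-entry, and row E's assumes a worsening that can be dated or joined. This should be corrected before the tables are programmed, but it does not call the study's safety data into question.

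**What to change.** In SAP 7.1:

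1. Define a TEAE flag with both protocol criteria and use it for category 3.
2. Restrict category 2 to AEs ongoing on Day 1 that did not worsen on treatment, or state that category 4 counts each event once. Otherwise a worsened AE would enter category 4 twice.
3. State which category an event joined under the same-event rule takes.
4. Date a worsening by the start of the 020 record that documents it, and name a default category where no usable date exists.
5. Define category 5 by onset only, as AEs starting after the cut-off, in line with the footnote to Table 14.3.2.15.1. This removes the circularity and keeps AEs with on-treatment onset in categories 3 and 4.
6. Use one cut-off in text and footnote: 7 days, or 14 days recorded as a change from the protocol.
7. Add an overall table and a SOC/PT table on category 3 plus category 5.

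Check against the nine courses, taking the first option in item 2: category 2 becomes {B, I}. With 14 days, category 3 is {C, D, E, F, G} and category 5 is {H}. With 7 days they are {C, D, E, F} and {G, H}. Either way the two together equal the protocol TEAE set.

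The cost is SAP wording, one derivation flag and two tables, plus a check of whether the 020 AE form yields a usable date for a change.

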After missing date imputation, if the end date and start date of two or more AEs with the same Preferred Term are less than or equal to two days apart, then the AE will be considered to be the same event and will be counted as one event. If the end date is missing for the first AE or the start date for the sequential AE is before the end date for the first AE, then the AEs will be considered one event and will be counted once. In every other case, the events will be counted separately.

The following summaries will be provided for AE categories 2-4 above:

- An overall summary of AEs summarizing the number and percent of subjects, and the number of unique AEs, in the following categories: any AE, severe AE, AE related to study drug, serious AE, related serious AE (serious adverse reaction or SAR), AE with outcome of death, adverse events of special interest (AESIs), AE leading to dose reduction, AE leading to dose interruption, AE leading to withdrawal of study drug, and AE leading to dose reduction, dose interruption, or withdrawal of study drug.
- Number of subjects who experienced AEs and total number of unique AEs by MedDRA SOC and PT.
- Number of subjects who experienced AEs by MedDRA SOC, PT, and worst severity.

- Number of subjects who experienced AEs by MedDRA SOC, PT, and strongest relationship to study drug (Related/Not Related). Events reported as “Possibly Related,” or “Related” will be included in the Related category. Events reported as “Unlikely Related” or “Not Related” will be included in the Not Related category. At each level of subject summarization a subject is classified according to the strongest relationship, as determined by the investigator, if the subject reported one or more events. AEs with a missing relationship will be considered related for this summary.
- Number of subjects who experienced serious AEs (SAEs) and total number of unique serious AEs by MedDRA SOC and PT (and subsets for fatal and nonfatal SAEs as well as related SAEs (SARs), as described above).
- Number of subjects who experienced severe AEs and total number of unique severe AEs by MedDRA SOC and PT. AEs with missing severity will be considered severe for inclusion in this summary.
- Number of subjects who experienced AEs leading to change in dose and total number of unique AEs leading to change in dose (dose reduction, dose interruption, and study drug withdrawal, separately and combined) by MedDRA SOC and PT.

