- Number of subjects who experienced unique protocol-specified AESIs and total number of unique protocol-specified AESIs by MedDRA SOC and PT.

The above summaries of AEs will also be presented for non-AChEI (acetylcholinesterase inhibitor)/Memantine users. Selected summaries of AEs will also be presented by diagnosis and prior study treatment. Depending on controlled study results, analyses of selected TauRx AE groupings may be undertaken.

A tabular summary of post-treatment adverse events (#5 above) by MedDRA SOC and PT will be provided.

The AE listing will include Prior AEs, All AEs, and Post-treatment AEs (#1, 4, and 5 above). Prior AEs, Pre-existing AEs and Post-treatment AEs will be flagged.

In addition, listings will also be provided for study-emergent or post-treatment SAEs (including subsets for fatal and non-fatal SAEs), study-emergent AEs leading to dose reduction, interruption or study drug withdrawal, and study-emergent or post-treatment AESIs. Post-treatment AEs will be flagged.

---

 Relationship is determined by the Investigator

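### SAP 7.1 leaves serious and fatal AEs starting more than 14 days after last dose out of every serious and fatal count, and its worsening clause also removes some events that began on drug

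*SAP*

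**What the plan says.** SAP 7.1 sorts AEs into five groups. Three definitions matter here.

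- Group 3 (study-emergent): "AEs that started on or after Day 1 of dosing in 020, excluding post-treatment AEs (defined in #5 below").
- Group 4 (all AEs) also leaves out post-treatment events: "note, this is a merge of #2 and 3 above".
- Group 5 (post-treatment) has two limbs. The first goes by onset: "The study-emergent AEs (3# above) that have an onset more than 14 days after the last dose of study drug". The second brings in events whatever their onset date, provided they get worse late: "or that worsen in intensity or treatment attribution following discontinuation more than 14 days after the last dose of study drug".

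The main tables are then introduced with "The following summaries will be provided for AE categories 2-4 above". Under that sentence come the overall summary (which has a row for AEs with outcome of death), the severity and relationship tables, the severe, dose-change and AESI tables, and the SAE table with "subsets for fatal and nonfatal SAEs as well as related SAEs (SARs), as described above". For group 5 the SAP promises one product: "A tabular summary of post-treatment adverse events (#5 above) by MedDRA SOC and PT will be provided". The shell for Table 14.3.2.15.1 has no rows for seriousness or outcome, and its footnote defines post-treatment AEs by onset alone. SAP 7.1 does provide by-subject listings of post-treatment SAEs (fatal and non-fatal) and AESIs, with post-treatment events flagged.

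Protocol 9.6.1 is built differently: "The subset of TEAEs that have an onset more than 7 days after the last dose of study drug will be considered post-treatment". There the post-treatment events remain TEAEs, and its overall summary counts serious TEAEs and TEAEs with outcome of death without stating any post-treatment exclusion.

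**The concern.** Long-term safety and tolerability is the only objective of this study that calls for evaluation, and the death and SAE counts are what readers will carry away. If a class of serious or fatal events is defined out of every table that counts them, those totals are too low, and nothing in the table titles says so. The fatal table for group 3, for example, is titled simply as events that started on or after Day 1 of dosing.

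The trial sets out to collect these events. Protocol Appendix A schedules a follow-up visit 28 (± 14) days after the last dose. Protocol 7.1 continues AE follow-up beyond that visit when needed, and protocol 7.1.6.1 asks for related SAEs found at any time after the study. Protocol section 9 also allows interim reports for safety reporting and regulatory submissions, which would carry the same counts.

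The worsening clause adds a second problem. It can take an event that began on drug out of the main tables because it later became more intense, or was later judged more related to drug.

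**Working it through.** The plan states no figure to reproduce. The check is to run test events through the definitions, then do day-count arithmetic on the follow-up window.

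**Circularity.** Group 3 is everything from Day 1 onward except group 5, and group 5 is a subset of group 3. An event that meets the late condition is in group 5 only if it is in group 3, and in group 3 only if it is not in group 5. No assignment satisfies both. The workable reading, used below, takes the word study-emergent in group 5 to mean onset on or after Day 1.

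**Test events** (all serious; days counted from last dose):

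| Event | Group under 7.1 text | In serious/fatal tables | In Table 14.3.2.15.1 by its footnote |
|---|---|---|---|
| Fatal, onset day +10 | 3 | Yes | No |
| Fatal, onset day +20 | 5 | No | Yes, without outcome |
| Onset on drug; intensity or attribution worsens day +20 | 5 | No | No |
| Onset on drug, already severe; death day +20, attribution unchanged | 3 | Yes | No |
| Pre-existing AE, worsens day +20 | 2 | Yes | No |

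The second row is the main gap. The third is the worsening clause: the text sends the event to group 5, but the group 5 table does not admit it, so it may be in no AE table. The fourth row follows from protocol 7.1 and 7.1.1, where intensity is mild, moderate or severe and outcome is a separate field. The SAP also merges records of the same preferred term no more than two days apart, without saying which group a merged event takes when the later record is the worsened one.

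**Share of planned off-drug follow-up beyond the 14-day cut** (visit at 28 ± 14 days):

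- Nominal visit: 28 − 14 = 14 of 28 days (50%).
- Latest visit: 42 − 14 = 28 of 42 days (67%).
- Earliest visit: 14 − 14 = 0 days.

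**Illustration of size.** The enrolment range of 1050 to 1400 is from the protocol synopsis. The 60% stopping drug and the mortality of 5% to 20% per year are assumptions; neither document gives these rates. Deaths in window = N × 0.60 × (uncounted days / 365.25) × annual rate.

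- N = 1050, 14 days: 630 × 14 / 365.25 = 24.1 subject-years; × 0.05 = 1.2; × 0.20 = 4.8.
- N = 1400, 14 days: 840 × 14 / 365.25 = 32.2 subject-years; × 0.05 = 1.6; × 0.20 = 6.4.
- N = 1400, every visit at day 42 (28 days): 64.4 subject-years; × 0.05 = 3.2; × 0.20 = 12.9.
- Every visit at day 14: 0.

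For given inputs these are upper bounds on deaths missing from the fatal tables over that window, because a death from an event with earlier onset mostly stays in group 3.

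**The case against.** The strongest reply is that nothing is hidden. Listings 16.2.7.2.1 to 16.2.7.2.3 cover post-treatment SAEs with their fatal and non-fatal subsets, the listing shells carry a post-treatment flag, and Listing 16.2.7.2.4 gives the date of death. With a handful of deaths, a reader could count them. Death is also a discontinuation reason in the disposition table. The study is single-arm and descriptive, so no comparison is biased. A lag after last dose is a common convention, and 14 days keeps more events as study-emergent than the protocol's 7 would.

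Much of this stands, and it limits the point. A reader might infer that late deaths vanish from the report; they do not, since they are listed and flagged. But a listing supplies no n (%) and does not correct the headline totals. Disposition need not record the death of someone who had already stopped for another reason, and it is not a fatal AE count. A lag is unobjectionable in itself; the trouble is that no serious or fatal table exists on the far side of it.

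A reader might also infer that any on-drug event that turns fatal after stopping leaves the fatal tables. The text does not say so: the clause is triggered by intensity or attribution, not by outcome. Nor is reassignment by worsening settled, because the footnote of Table 14.3.2.15.1 contradicts it.

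Finally, it is tempting to say that deaths cluster just after stopping. Protocol 5.3 does let investigators stop drug because a subject is worsening, which makes it plausible, but neither document gives a rate.

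**Conclusion.** The concern holds in this form. Serious or fatal study-emergent AEs with onset more than 14 days after last dose are listed and flagged but enter no serious or fatal AE count. That departs from protocol 9.6.1, where they remain TEAEs. SAP section 9 records no such change and only defers to the study report. Separately, the worsening clause cannot be programmed as written: it is circular with group 3, it conflicts with the shell footnote, and it can leave an event that began on drug in no AE table.

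The defect follows from the definitions and needs no rate. Its size cannot be computed from the documents. On the stated assumptions it is about 1 to 6 deaths at the nominal visit, none if every visit falls at day 14, and up to about 13 with 1400 subjects all seen at day 42. Pre-existing AEs that worsen late are unaffected. This should be corrected before database lock.

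**What to change.** 1. Delete the worsening clause from group 5 and assign AEs by onset date only, as the footnote of Table 14.3.2.15.1 already does.
2. Remove the circularity: define group 3 as onset from first 020 dose up to the cut-off after last dose, and group 5 as onset after it, neither by reference to the other.
3. Reconcile the protocol's 7-day and the SAP's 14-day cut-off, use one throughout, and record the change in SAP section 9.
4. Produce the overall, serious and fatal tables also for groups 3 and 5 combined, or add serious and fatal rows to Table 14.3.2.15.1. Either way, add an all-cause death count.

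The cost is SAP wording and a few repeats of existing shells; no new data are needed. Reported death and SAE counts will rise slightly.
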